5.8.3 IUDR incorporation in granulocytes

5.8.3.1 Specimen(s) Receipt and Processing at the [name] Laboratory

Upon receipt of fresh blood specimens in EDTA, [name] laboratory will accession and barcode the samples prior to processing. Processing will be according to the methodology described in Section 2.5.4, including granulocyte isolation using a histopaque (Sigma Chemical Co., St. Louis, MO) 1077/1119 gradient.

5.8.3.2 Site Performing Correlative Study

This study will be performed under the supervision of [name] in the Clinical Pharmacology Branch at DTP, DCTD.

6. TREATMENT PLAN

6.1 Agent Administration

Treatment will be administered on an outpatient basis. Reported AEs and potential risks are described in Section 10. Appropriate dose modifications are described in Section 7. No investigational or commercial agents or therapies other than those described below may be administered with the intent to treat the patient's malignancy.

6.1.1 IPdR dose escalation schema

This is a phase 1 dose escalation study that consists of two parts, Part IA and Part IB. Part IA uses an accelerated titration design with a single patient cohort, and a 100% dose escalation between patient cohorts until a treatment related Grade 2 non-hematologic toxicity or grade 3 neutropenia or thrombocytopenia is observed. The accelerated titration design may reduce the number of patients potentially undertreated by receiving PO IPdR doses that are not expected to result in clinically relevant radiosensitization. After the completion of part 1A, the protocol will

be amended to incorporate the dose levels for part 1B. Part IB will commence when toxicity is encountered in Part IA. Cohorts of 3-6 patients will be entered per dose level until dose-limiting (DLT) is reached, and the MTD is defined. An IPdR dose of 2400 mg QD is the maximum allowed dose. Dose escalation between dose levels will be adjusted to accommodate the availability of 75mg and 600mg IPdR capsules.

Part IA:

An initial single patient dose escalation of twice daily PO IPdR × 38 days with concomitant capecitabine (825 mg/m²/BID Monday morning through Friday evening on RT days) will be conducted in Part IA. Dosing will be based on the patient's assigned dose level. The starting dose is 75 mg BID (Dose 1) × 38 days ($\geq 1/10^{\text{th}}$ MTD in ferrets, as previously determined [Kinsella *et al.*, 2000]). A 100% dose escalation will be used until a treatment related Grade 2 non-hematologic toxicity or grade 3 neutropenia or thrombocytopenia is observed. Two additional patients will then be entered at this dose level. If a second patient of these 3 patients experiences a treatment related Grade 2 systemic toxicity (or if a single patient develops treatment related \geq grade 3 toxicity), then a stop/switch rule is invoked for Part IA and Part IB of the dose escalation scheme commences. If not, the dose is incremented to the next level in Part IA (after each patient is evaluated for 4 weeks of follow up to assess acute toxicity).

Definitions of “Dose-limiting” and “Moderate” toxicities for Part IA (for exceptions see Section 6.2)

Grade 2 non-hematologic	Moderate
Grade 3 non-hematologic	DLT
Grade 4 non-hematologic	DLT
Grade 2 ANC and/or Plt	Moderate
Grade 3 ANC and/or Plt	Moderate
Grade 4 ANC and/or Plt	DLT

In part IA, if a patient develops:

- a DLT, the stop/switch rule is invoked, and part IB commences
- a “moderate” toxicity, two additional patients will be entered at this dose level, and if
 - one of these patients develops a DLT, the stop/switch rule is invoked, and part IB commences
 - one of these patients develops a “moderate” toxicity, the stop/switch rule is invoked, and part IB commences
 - neither of the two additional patients develops a DLT or “moderate” toxicity, part IA recommences at the next dose level

A patient will be considered unevaluable if they receive $<67\%$ of their total intended dose of any study treatment (IPdR, capecitabine, or RT) for non-protocol required reasons. Patient medication diaries and RT documentation will be reviewed as each patient comes off-study to determine the actual total doses of each study treatment they received. If a patient is deemed unevaluable by this definition, they will be replaced by a new patient to be treated at the same intended dose level.

Part IA dose escalation schema			
Dose Level	Total radiation Gy (45 Gy primary field, 5.4 Gy [contact] Gy/fraction/day)	Capecitabine (mg/m² BID)	IPdR (mg BID) Administered throughout radiation
1A	50.4	825 mg/m ² BID	75 mg BID
2A	50.4	825 mg/m ² BID	150 mg BID
3A	50.4	825 mg/m ² BID	300 mg BID
4A	50.4	825 mg/m ² BID	600 mg BID
5A	50.4	825 mg/m ² BID	1,200 mg BID

BID – Twice Daily, RT – Radiation therapy

Part IA is closed to further accrual.

Part IB:

Under Part IB of this protocol, cohorts of 3-6 patients will be entered per dose level. In Part IB, 3 patients will initially be accrued to a dose level. If 0 of 3 patients do not experience grade 3 non-hematopoietic or grade 4 hematopoietic/GI DLT, then dose escalation will proceed. If a DLT is observed in one of the first 3 patients in a dose level cohort, the cohort will be expanded to a maximum of 6 patients.

Part IB dose escalation schema			
Dose Level	Total radiation Gy (45 Gy primary field, 5.4 Gy [contact] Gy/fraction/day)	Capecitabine (mg/m² BID)	IPdR (mg QD) Administered throughout radiation^{1,2}
1B	50.4	825 mg/m ² BID	75mg QD
2B	50.4	825 mg/m ² BID	150mg QD
3B	50.4	825 mg/m ² BID	300mg QD
4B	50.4	825 mg/m ² BID	600mg QD
5B	50.4	825 mg/m ² BID	1200mg QD
6B	50.4	825 mg/m ² BID	1800mg QD
7B	50.4	825 mg/m ² BID	2400mg QD

QD – Once Daily, BID – Twice Daily, RT – Radiation therapy

¹ The maximum allowed dose of IPdR is 2,400mg QD

² Actual doses will be rounded to account for availability of only 75 mg and 600 mg IPdR capsules

Patients will be assessed 4 weeks following completion of study treatment (Week 10 unless there were delays in therapy). This will be the final assessment for study-related toxicity. Patients will undergo surgical resection 8-12 weeks following completion of chemoRT (IPdR), and study-related response will be assessed at that time.

Regimen Description					
Agent	Premedication; Precautions	Dose	Route	Schedule	Study Length
IPdR	Take on an empty stomach, either 1 hour before or 2 hours after meals.	Dose as appropriate for the assigned dose level.	PO	QD ^A	38 days (6 weeks)
Capecitabine	Take within 30 minutes after a meal (breakfast and dinner).	825 mg/m ² ^C	PO	BID Monday morning through Friday evening on RT days ^{B,C}	
RT		1.8 Gy/fraction/day × 28 doses (50.4 Gy total dose)		5 doses per week until week 5 and 3 doses during Week 6 ^D	

^AOn the days of radiation therapy, the daily dose of IPdR will be administered within 30 min - 2 hours prior to radiation. Patients may take dose at home if the timing allows.

^BCapecitabine will be taken Monday morning through Friday evening each week of RT.

^CDosing will be with 150 mg and 500 mg tablets

^DRT will be given only Monday through Friday

QD – Once Daily, BID – Twice Daily, PO – Oral, RT – Radiation therapy

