6.2 Definition of Dose-Limiting Toxicity

Management and dose modifications associated with the above AEs are outlined in Section 7.

DLTs will be captured until 4 weeks after completion of IPdR therapy and will be graded according to the CTCAE v5.0. DLTs will be defined as clinically significant grade 3 or 4 toxicities possibly or probably related to study treatment.

- Grade 4 neutropenia (ANC < 500/mm³)
- Grade 4 electrolyte toxicities
- ANC <1000/mm³ with fever (temp >101 F) or infection
- Grade 4 thrombocytopenia: Platelets <25,000/mm³
- Platelets <50,000/mm³ requiring transfusion
- Grade 3 or 4 treatment related non-hematologic toxicities excluding alopecia.
- Patients who receive <67% of intended IPdR secondary to treatment related toxicities will also be considered as having a DLT

In addition, during chemoradiation, DLTs will also include AEs requiring interruptions of radiation for >5 consecutive scheduled fractions (and / or ≥ 9 total scheduled fractions) or for >10 consecutive scheduled doses of capecitabine (and / or ≥ 19 total scheduled doses of capecitabine). The following AEs will not be considered DLTs:

- Any grade of alopecia,
- Grade 3 arthralgia or myalgia,
- Brief (<1 week) grade 3 fatigue,
- Grade 3 fever,

- Grade 3 diarrhea or vomiting responding to supportive care
 - Grade 3 nausea, vomiting or diarrhea will be considered a DLT if it occurs for greater than 48 hours despite maximal medical support.
- Grade 3 radiation dermatitis,
- Grade 3 or 4 electrolyte abnormalities will not be considered DLTs if the electrolyte disorder can be corrected to grade 2 or less within 72 hours.

All patients who have received at least one dose of IPdR are evaluable for toxicities.

For dose escalation decisions, patients should have completed $\geq 80\%$ of the planned chemoradiation doses unless the reason for discontinuation is an AE that qualifies for DLT.

Dose escalation will proceed within each cohort in Part IB according to the following scheme. DLT is defined above.

Number of Patients with DLT at a Given Dose Level	Escalation Decision Rule
0 out of 3	Enter 3 patients at the next dose level.
≥ 2	Dose escalation will be stopped.

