1 out of 3	Enter 3 more patients at this dose level. 
• If 0 of these 3 patients experience DLT, proceed to the next dose level.• If 1 or more of this group suffer DLT (i.e. 2 of 6 patients), then dose escalation is stopped, and this dose is declared the maximally administered dose.
≤ 1 out of 6 at highest dose level below the maximally administered dose	This is generally the recommended phase 2 dose. At least 6 patients must be entered at the recommended phase 2 dose.

During the MTD dose finding portion, patients who are removed from study for reasons other than a DLT will be replaced.

6.3 Dose Expansion Cohorts:

For the expansion cohort, patients will continue to be monitored for occurrence of DLT. Three additional patients will be treated at the dose level below the dose associated with DLT to establish the MTD. The MTD is defined as the dose below which 2 or more of 3 to 6 patients experience DLT. The MTD will be deemed to be RP2D if $\geq 80\%$ of the patients are able to receive $\geq 80\%$ of the planned treatment doses. Monitoring of all safety and toxicity data is done by the Principal Investigator and the Corresponding Organization on a real-time basis as data are entered into Medidata Rave using the Web Reporting Module. All participating sites are expected to notify the Principal Investigator when a DLT has occurred.

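### Section 6.1.1 words the Part IB escalation rule as a double negative that contradicts the Section 6.2 table: a minor inconsistency with a cost-free correction

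*Combined protocol and SAP*

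**What the plan says.** The Part IB rule appears in two places.

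Section 6.1.1 (Part IB paragraph) enters three patients at a dose level and then says: "If 0 of 3 patients do not experience grade 3 non-hematopoietic or grade 4 hematopoietic/GI DLT, then dose escalation will proceed". The next sentence reads: "If a DLT is observed in one of the first 3 patients in a dose level cohort, the cohort will be expanded", up to a maximum of six. Section 6.1.1 gives no instruction for two or three DLTs in the first three patients.

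Section 6.2 introduces its table with: "Dose escalation will proceed within each cohort in Part IB according to the following scheme. DLT is defined above". Its rows are:

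- 0 out of 3 with DLT: "Enter 3 patients at the next dose level".
- 2 or more with DLT: "Dose escalation will be stopped".
- 1 out of 3 with DLT: three more patients at the same level, then "If 0 of these 3 patients experience DLT, proceed to the next dose level"; one or more further DLTs stops escalation.

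On timing, Section 6.1.1 says for Part IA that the dose goes up "after each patient is evaluated for 4 weeks of follow up to assess acute toxicity". The Part IB paragraph does not repeat this. Section 6.2, without limiting itself to one part, says: "DLTs will be captured until 4 weeks after completion of IPdR therapy". Sections 6.1.1 and 6.8 and the Section 11 calendar place the final toxicity assessment 4 weeks after treatment, at Week 10 if there are no delays.

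**The concern.** The 6.1.1 sentence counts patients who do not have a DLT and escalates when that count is zero. Zero patients without a DLT means three patients with one. As written, the treatment plan therefore escalates after the most toxic result a cohort of three can give, and gives no instruction after the cleanest. Section 6.2 directs the opposite in both cases.

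Part IB is the part still open to accrual, and it sets the MTD, the first primary objective (Section 1.1.1). A reader who goes to 6.1.1 for the escalation rule should not find the reverse of the table that governs it. Because 6.1.1 has no stopping instruction of its own, nothing in that paragraph tells the reader what to do at two or three DLTs. The correction has to come from another section.

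**Working it through.** The plan states no figure for this rule, so there is none to reproduce. The check compares the two texts over every possible result.

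**Inputs.** Let *d* be the number of the first three patients with a DLT. The literal 6.1.1 condition is 3 − *d* = 0. The 6.1.1 expansion sentence applies at *d* = 1. The 6.2 table escalates at *d* = 0, adds three at *d* = 1 and stops at *d* ≥ 2.

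| DLTs in first 3 | DLT-free | Literal 6.1.1 | Section 6.2 table | Comparison |
|---|---|---|---|---|
| 0 | 3 | condition not met; no instruction | escalate | differ |
| 1 | 2 | expand, up to 6 | add 3 patients | agree |
| 2 | 1 | condition not met; no instruction | stop | neither escalates; only the table says stop |
| 3 | 0 | condition met; escalate | stop | contradict |

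The direct contradiction is at 3 of 3. At 0 of 3 the literal text omits the instruction that the table gives. At 2 of 3 it is also silent, but no escalation follows under either text.

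**Direction of the literal rule.** With a true DLT probability *p*, the chance of escalating straight from the first three patients is *p*³ under the literal sentence and (1 − *p*)³ under the table. The documents give no DLT rate for this purpose, so the values of *p* are assumed:

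| Assumed *p* | Literal 6.1.1, *p*³ | Section 6.2, (1 − *p*)³ |
|---|---|---|
| 0.1 | 0.001 | 0.729 |
| 0.3 | 0.027 | 0.343 |
| 0.5 | 0.125 | 0.125 |
| 0.6 | 0.216 | 0.064 |

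The literal rule escalates more often as toxicity rises. This shows only that the wording is inverted; it does not forecast what the trial will do.

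**With the wording corrected.** If the condition becomes *d* = 0, Section 6.1.1 agrees with the table at 0 of 3 (escalate) and 1 of 3 (expand), and nothing in it conflicts with the stop at 2 or 3.

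**Timing.** Without delays, IPdR ends on Day 38. The DLT window closes at Day 38 + 28 = Day 66, which lies in Week 10 (Days 64–70). The window in 6.2 and the final toxicity visit therefore coincide.

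**The case against.** The strongest reply is that this is a slip of the pen. Section 6.2 says in terms that its scheme governs Part IB, and the scheme is clear. The next sentence of 6.1.1 expands the cohort after a single DLT, which makes no sense if three DLTs lead to escalation. The 1-out-of-3 row of the table words the same condition correctly. Section 13.1 requires Principal Investigator sign-off on every escalation, and Section 6.3 expects sites to report each DLT to that investigator. All of this stands, and it is why the point is minor. It does not make the sentence correct: an inverted rule in the live treatment plan still needs changing.

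A reader might go further and infer that Part IB has no 4-week toxicity wait, because that wait is spelled out only for Part IA. The documents do not support that. The capture period in 6.2 is not confined to one part, and the Part IB table is tied to that DLT definition. A count of 0 out of 3 is therefore not final until the window closes, and the Week 10 assessment is described directly after the Part IB schema. A full-window count is the natural reading. No sentence expressly bars opening the next level sooner, but nothing shows that early escalation is planned. The documents fix no other decision time, so no rate of missed DLTs can be derived from them.

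**Conclusion.** The point holds as a minor internal inconsistency in an operative decision rule. The literal 6.1.1 sentence escalates only at 3 of 3 and is silent at 0 of 3, against a table that stops at the first and escalates at the second. This rests on the wording alone and needs no assumed DLT rate.

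A reader might also infer that the design itself escalates on toxicity, or that patients are likely to be moved up after three DLTs. Neither follows. The intended rule is plain from the next sentence and from the 6.2 table, and sign-off stands between the text and any escalation. No design choice is in question. The absence of a restated wait for Part IB is not an error; stating it would only be a clarification.

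**What to change.** Replace the 6.1.1 condition with wording such as: *If none of the first 3 patients experiences a DLT as defined in Section 6.2, escalate to the next dose level.* This costs nothing and changes no intended decision.

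Pointing to Section 6.2 has a side benefit. The 6.1.1 sentence mentions only grade 4 for hematopoietic events, whereas 6.2 also counts ANC below 1000/mm³ with fever or infection, and platelets below 50,000/mm³ requiring transfusion. By 6.2's own grade 4 cut-offs (500 and 25,000/mm³), some of those events fall short of grade 4.

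As an optional clarification, Part IB could add that the next level opens once each counted patient has either had a DLT or completed the 4-week assessment after IPdR. This costs nothing if the full window is already awaited, as the text implies.

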6.1.2 IPdR administration

- Method of delivery is by oral administration in capsule form BID × 38 days for Part IA and once daily for Part IB (Week 6).
- Dosing will be based on the patient's assigned dose level.
- The initial drug dose is 75 mg BID.
- The capsules will be taken on an empty stomach (*i.e.* either 1 hour before or 2 hours after meals).
- On the days of radiation therapy, the daily dose will be administered within 30 min - 2 hours prior to radiation and can be taken at home if timing allows.
- Assessment of compliance with treatment: Patients will be instructed to keep a medication log, recording the date, time and numbers of capsules of each dose (See Appendix D)

6.1.3 Capecitabine

6.1.3.1 Dose and Schedule

Capecitabine should be dosed at 825 mg/m² PO BID on days of radiation only. The usual radiation schedule will be Monday through Friday, and in that case, the first capecitabine dose of the week will be taken on Monday morning, and the last dose of the week will be taken on

Friday evening. Dosing will be with 150 mg and 500 mg tablets to achieve a dose as close as possible to 825 mg/m². Additional dose adjustments will be made as needed. At the discretion of the treating physician, the body surface area (BSA) may be capped at 2.20 – 2.25 for calculating capecitabine dosage (optional). Please refer to package insert for exact dose calculation details.

6.1.3.2 Guidance for Administration:

Capecitabine is to be taken roughly 12 hours apart at approximately the same times each day with about 200 ml of water within 30 minutes after a meal. Capecitabine tablets should be swallowed as whole and should not be crushed or cut. Capecitabine tablets should be stored at room temperature (15° to 30° C) in the container in which they are provided.

6.1.4 Radiation therapy

Radiation Therapy Schema:

The treatment is delivered in 2 phases, an initial phase to treating the entire PTV_4500 including the PTV_5040 volume to 45 Gy, followed by a boost phase, treating the PTV_5040 with an additional 5.4 Gy to a total of 50.4 Gy. The fraction size is 1.8 Gy for all phases.

Phase	Target	Dose (Gy)	Number of Fractions	Fraction Size	Rx Length	Rx Days
Initial	PTV_4500	45	25	1.8 Gy	5 weeks	Monday through Friday
Boost	PTV_5040	5.4	3		3 days	
Total		50.4	28			

6.1.4.1 Treatment technology

This protocol allows, but does not require, the use of Intensity Modulated Radiation Therapy (IMRT). This protocol requires treatment with photons with minimum nominal energy specification of 6 MV. IMRT is allowed and can be used either with static gantry or arcs (VMAT). Tomotherapy delivery is allowed.

6.1.4.2 Immobilization and simulation

Immobilization

Proper immobilization is important for this protocol. Patient setup reproducibility must be achieved using appropriate clinical devices. A custom immobilization device (such as Alpha Cradle or Vac-Loc for supine patients and an Alpha Cradle with bowel displacement device for prone patients) is suggested to minimize set-up variability. Simulation may be done with the patient in the supine "arms up" position for patients with very thin body habitus or the prone

"arms up" position for patients of moderate or large body habitus.

Simulation imaging

CT Simulation is required, and the images must be acquired using a CT-simulator with a slice thickness ≤ 3 mm. Care should be taken to use the smallest possible FOV that contains the entire surface of the patient with a 512×512 image matrix. Oral CT contrast is strongly suggested. An anal marker at the verge is required. The CT simulation must be performed with the patient in the treatment position.

Typical CT scan limits are mid-femur inferiorly to include the L2 vertebral body superiorly. The CT scan needs to include the following structures in their entirety: Treatment volumes (PTVs), bladder, and femoral heads.

6.1.4.3 Definition of target volumes and margins

Note: All structures must be named for digital RT data submission as listed in the table below. The structures marked as "Required" in the table must be contoured and submitted with the treatment plan. Structures marked as "Required when applicable" must be contoured and submitted when applicable.

Resubmission of data may be required if labeling of structures does not conform to the standard DICOM name listed. Capital letters, spacing and use of underscores must be applied exactly as indicated.

The volumes are to be defined by planning CT/MRI techniques as well as PET scans when clinically appropriate. While PET scans are not mandated as part of the protocol, for those patients who have PET scans available, the information may be used to aid in treatment planning. The inferior extent of palpable tumors should be determined by physical examination.

Examples of contoured patients (anorectal atlas) are available for review on the NRG Oncology website (<https://www.nrgoncology.org/Resources/Contouring-Atlases>). These examples are excellent resources for the contouring of normal structures as well as GTV, CTV, and PTV design, and their use is strongly encouraged.

Standard Name	Description	Validation
GTV_5040	GTV to receive 50.4 Gy	Required
PTV_5040	PTV to receive 50.4 Gy	Required
CTV_4500	CTV to receive 45 Gy	Required
PTV_4500	CTV to receive 45 Gy	Required

Detailed specification:

Gross tumor volume (GTV): This includes the primary tumor and any pelvic nodes felt involved grossly with metastatic disease. Assessment of the primary tumor and nodal disease may be made on the basis of endoscopy, CT, PET-CT, MRI, or transrectal ultrasonography. The entire rectal circumference at the level of the tumor should be included as GTV_5040.

Clinical target volume (CTV_4500): This includes the GTV and the following nodal groups: perirectal nodes; presacral nodes; internal iliac; and common iliac nodes below the L5-sacral junction.

Planning target volume 4500 (PTV_4500): This will provide a margin around the CTV_4500 to compensate for the inter- and intra-fraction uncertainty consequent to daily setup uncertainty and to potential internal organ motion. By definition, the PTV_4500 will consist of a symmetrical 7 mm expansion around the CTV_4500. In the event that a PTV_4500 extends outside of the skin surface, the clinician should manually trim the PTV_4500 contours to be 3 mm inside the outer skin (unless there is direct skin involvement).

The following are guidelines for generating the CTV_4500 and PTV_4500 and PTV_5040. The CTV_4500 can be formed from the following CTV sub-volumes:

- CTV_rectal (CTV_4500) = Rectal GTV +1.5 cm radially, +2.5 cm craniocaudally along the mucosal surface. The radial expansion can be shrunk to within the mesorectal fascia and off organs/sidewall if no clinical/radiographic evidence of an involved mesorectal fascia OR T4 disease.
- CTV_nodal (CTV_4500) = Nodal GTV + 1.5cm symmetrical expansion. The symmetric expansion can be shrunk to within the mesorectal fascia and off organs/sidewall if no clinical/radiographic evidence of an involved mesorectal fascia.
 - External iliac LNs are to be included in CTV_4500.
 - Inguinal LN basins will not be included in the CTV_4500 or CTV_5040 volume in low-lying rectal cancer except in patients with high likelihood of pathologic involvement by MRI or PET/CT imaging. A LN biopsy of inguinal LNs is not recommended.
- CTV_vessels = Uninvolved iliac vessels + 1.0 cm. This expansion can be trimmed off pelvic sidewall/bowel.
- CTV_presacral = the entire sacral hollow from mid S1-S5 and 8 mm tissue anterior to the anterior border of the sacral bone.
- CTV_perirectal (CTV_4500) = The mesorectum and perirectal lymphatic CTV should be identified on cross-sectional imaging and is best seen on an MRI. If the fascia cannot be confidently visualized, it can be generated by utilizing anatomic landmarks:
 - Posterior Border: anterior border of the sacrum and gluteus maximus
 - Lateral Border: ileum, piriformis and obturator muscles
 - Anterior Border: should include the interface with the bladder, vagina, uterus or prostate
 - Inferior Border: the levators. The caudal extent of CTV_4500 is the pelvic floor/levators. If there is radiographic evidence of extension into the ischiorectal fossa, the CTV_4500 will extend to 2-3 mm beyond the levator muscles. For very

advanced cT4 tumors extending through the levators, a 2-cm margin up to bone is recommended.

- The PTV_4500 is generated by expanding all of the above structures by 0.7 cm symmetrically and unifying them into one 3-dimensional volume for planning purposes.
- The PTV_5040 is an expansion of the GTV_5040 by 3 cm and the presacrum, this volume should not extend beyond PTV_4500.

